Structure: Multicenter, randomized, double-blind, placebo-controlled, parallel-group, single attack study; randomization to placebo, ubrogепant 25 mg, or ubrogепant 50 mg.

Duration: The study includes a screening period of up to 14 days prior to randomization, a 60-day period in which to treat a single migraine attack, and a 4-week follow-up period.

Study Treatment Groups: Ubrogепant 25 mg, ubrogепant 50 mg

Controls: Ubrogепant placebo

Dosage/Dose Regimen: Study participants will have up to 60 days to treat a single qualifying migraine attack of moderate or severe headache pain intensity at home. Patients have the option to take a second dose of investigational product (IP) or rescue medication if the patient has either a nonresponding migraine or a migraine recurrence.

[Redacted]

[Redacted]

[Redacted]

Study Population Characteristics

Number of Patients: Approximately 1650 patients will be randomized (550 per treatment arm)

Condition/Disease: Migraine with or without aura

Key Inclusion Criteria: To be eligible for study participation, patients must be 18 to 75 years of age (inclusive), have a history of migraine with or without aura for at least 1 year consistent with a diagnosis according to the International Classification of Headache Disorders criteria, 3rd edition, beta version (ICHHD-3 beta, 2013) and experience between 2 to 8 migraine attacks with moderate to severe headache pain in each of the 3 months prior to Screening (Visit 1).

Key Exclusion Criteria: [Redacted]

Response Measures

[figure not shown]
Efficacy: Rating of headache severity, absence or presence of migraine-associated symptoms, use of rescue medication, use of optional second dose, and recurrence of headache pain

[figure not shown]
[Redacted]

[figure not shown]
General Statistical Methods and Types of Analyses: The efficacy analyses will be based on the Modified Intent-to-treat (mITT) Population. The last observation carried forward (LOCF) approach will be used to impute missing posttreatment values. Baseline for efficacy is defined as the last nonmissing efficacy assessment before the initial dose of study treatment. For each primary variable, the observed response proportions will be provided by treatment group. The primary efficacy variable of pain freedom at 2 hours after the initial dose will be analyzed using a logistic regression model with categorical terms for treatment group, historical triptan response (triptan responder, triptan insufficient responder, or triptan naïve), use of medication for migraine prevention (yes/no), and baseline headache severity (moderate or severe). The primary efficacy variable of absence of the most bothersome symptom at 2 hours after the initial dose will be analyzed using a similar logistic regression model with an additional categorical term for the underlying symptom that was identified as the most bothersome. The respective comparisons of the ubrogepant doses versus placebo, which are the formal tests of the efficacy hypotheses, will be conducted using the appropriate pairwise contrasts within the logistic regression model. For secondary and other efficacy endpoints related to migraine headache pain severity and/or recurrence, migraine-associated symptoms, or use of rescue medication (including the second dose of IP), the observed response proportions will be analyzed using the same methods used to analyze the primary efficacy variables. For secondary efficacy endpoints on migraine-associated symptoms, baseline presence/absence of the symptom will be included as an additional covariate for the logistic regression model. The proportion of patients reporting satisfaction with study medication at 2 and 24 hours after the initial dose, the proportion of patients able to function normally at 1, 2, 4, and 8 hours after the initial dose, and the proportion of patients assessed by the PGIC as “much better” or “very much better” at 2 hours after the initial dose will be analyzed using the same methods used to analyze the primary efficacy variables. The baseline functional disability score will also be included as a covariate for the analysis of the proportion of patients able to function normally. For the change from baseline in EQ-5D-5L index value at 24 hours after the initial dose, treatment comparisons of ubrogepant dose groups versus placebo will be performed using an analysis of covariance (ANCOVA) model with categorical terms for treatment group, baseline severity, historical triptan response, and use of medication for migraine prevention, and with the baseline EQ-5D-5L index value as a covariate. Descriptive statistics will be provided for the change from baseline in the EQ VAS score at 24 hours after the initial dose by treatment group.

[figure not shown]
[Redacted]

[figure not shown]
[Redacted]

1. Background and Clinical Rationale

What is Migraine and How Prevalent is It?

Migraine affects 18% of women and 6% of men in the United States with a peak prevalence occurring between the ages of 25 to 55 years. Approximately one-third of migraineurs have 3 or more migraine headaches per month, and over half report severe impairment or the need for bed rest during an attack (Lipton et al, 2007). In the United States, work loss due to migraine is estimated to cost ~ \$13 billion annually (Hu et al, 1999). Prevalence is similar in Europe, with migraine headache affecting 17.6% of women and 8% of men (Stovner and Andree, 2010). It is currently ranked by the World Health Organization as 19th among causes of disability (Katsarava et al, 2012).

Migraine is typically characterized by attacks of throbbing, unilateral headache of moderate or severe pain intensity, associated with nausea, vomiting, and/or sensitivity to light (photophobia) and sound (phonophobia). In about 25% of individuals, migraine headache may be preceded by focal neurological dysfunction (aura). Improving the diagnosis and optimizing treatments for migraine have been recognized as critically important to reduce the global burden of migraine (Katsarava et al, 2012).

Because there are no biological markers for migraine, diagnosis is based on clinical history, exam, and the exclusion of other headache disorders. Physicians apply clinical criteria to guide diagnoses and subsequent treatment. Episodic migraine is a syndrome diagnosis applied to patients with migraine (with or without aura) who have 1 to 14 headache days per month. Chronic migraine is a specific International Classification of Headache Disorders criteria, 3rd edition beta version (ICHD-3 beta) diagnosis applied to a subset of patients with ≥ 15 headache days per month (ICHD-3 beta, 2013; Katsarava et al, 2012; Olesen et al, 2006).

What is CGRP and What is its Relationship to Migraine?

CGRP (calcitonin gene-related peptide) is a neuropeptide implicated in the pathophysiology of migraine. CGRP levels in the cranial venous outflow (ie, external jugular vein) are increased during a migraine attack (Goadsby and Edvinsson, 1993) and exogenously administered CGRP has been shown to trigger migraine-like headache in migraineurs. The majority (80% to 90%) of trigeminal A δ fibers that innervate the dura contain CGRP, suggesting that these fibers may be involved in sterile neurogenic inflammation and migraine pain transmission. Furthermore, the CGRP receptor is present on human meningeal and cerebral blood vessels. These observations suggest that activation of the

trigeminovascular system, with release of CGRP, may play a key role in migraine pathogenesis and that inhibition of CGRP function may yield a novel therapeutic approach to treating migraine.

Establishment of CGRP Antagonism to Treat Migraine

The ability of CGRP antagonism to relieve pain in the acute treatment of migraine was established by using an intravenous (IV) formulation of olcegepant ([Olesen et al, 2004](#)), and replicated by Merck & Co., Inc with an oral formulation of telcagepant, a highly selective CGRP receptor antagonist (CGRP RA). In Phase 3 studies, telcagepant was superior to placebo in the primary endpoints of 2-hour pain freedom, 2-hour pain relief, and the absence of associated symptoms (photophobia, phonophobia, and nausea), as well as the key secondary endpoint of 24-hour sustained pain freedom ([Connor et al, 2009](#)). Serum alanine aminotransferase (ALT) increases were observed with telcagepant as well as with a second CGRP antagonist, MK-3207. For this reason, the development of these compounds was stopped.

What is Ubrogapant?

Ubrogapant, a novel CGRP receptor antagonist that is chemically distinct from both telcagepant and MK-3207, is now being developed for the acute treatment of migraine. Preclinical and clinical studies conducted to date for ubrogapant have shown no evidence of hepatotoxicity.

A Phase 2b clinical study was conducted, which compared 1-, 10-, 25-, 50-, and 100-mg doses of ubrogapant to placebo in the acute treatment of migraine. Overall, all the ubrogapant doses tested were well tolerated and the adverse event (AE) profile of all ubrogapant doses did not differ significantly from placebo. For the primary efficacy endpoint of pain freedom at 2 hours, ubrogapant doses of 1 and 10 mg did not differ from placebo, but doses of 25, 50, and 100 mg were better than placebo. For the primary efficacy endpoint of pain relief at 2 hours none of the ubrogapant doses differed from placebo, probably due to a high placebo response rate.

The absence of migraine-associated symptoms of photophobia, phonophobia, and nausea was assessed as key secondary endpoints. Ubrogapant doses of 50 and 100 mg were significantly better than placebo for absence of phonophobia and photophobia at 2 hours, whereas 25 mg did not differ from placebo. None of the ubrogapant doses differed from placebo for the endpoint of absence of nausea at 2 hours. Measures of sustained migraine headache relief

(2 to 24 hours and 2 to 48 hours sustained pain freedom and sustained pain relief) generally suggested that ubrogepant 50 mg and 100 mg were more effective than the 25-mg dose.

The purpose of this study will be to assess the safety and efficacy of 2 doses of ubrogepant, 25 and 50 mg, versus placebo in the acute treatment of migraine with or without aura, in a randomized, double-blind, placebo-controlled Phase 3 study.

2. Study Objectives and Clinical Hypotheses

2.1 Study Objectives

To evaluate the efficacy, safety, and tolerability of 2 doses of ubrogepant (25 and 50 mg) compared to placebo for the acute treatment of a single migraine attack.

2.2 Clinical Hypotheses

1. At least 1 ubrogepant dose is superior to placebo in the acute treatment of migraine.
2. Ubrogapant is safe and tolerable.

3. Study Design

This multicenter, randomized, double-blind, placebo-controlled, parallel-group, single attack study will enroll approximately 1650 patients from approximately 100 centers in the United States. Patients will be randomized (1:1:1) to 1 of the following 3 treatment groups: placebo, ubrogepant 25 mg, or ubrogepant 50 mg.

Study participants will have up to 60 days to treat a single qualifying migraine attack of moderate or severe intensity at home. Patients unable to treat a qualifying migraine within this time will be discontinued from the study.

[REDACTED]

The planned efficacy assessments are rating of headache severity, absence or presence of migraine-associated symptoms, use of rescue medication, use of optional second dose, and

recurrence of headache pain. A list and description of each efficacy assessment is in [Section 6.1](#) and the efficacy analyses are presented in [Section 7.3.1](#).

The planned safety assessments are AEs, clinical laboratory tests, electrocardiograms (ECGs), vital signs, physical examination, and the Columbia-Suicide Severity Rating Scale (C-SSRS). Details regarding safety assessments are described in [Section 6.5](#) and the safety analyses are presented in [Section 7.3.3](#).

[REDACTED]

[REDACTED]

[REDACTED]

3.1 Adjudication Committee and Data Safety Monitoring Board

An Adjudication Charter will be established and will describe the process for the blinded surveillance, monitoring, and adjudication by the Clinical Adjudication Committee of events of posttreatment elevations of ALT and/or aspartate aminotransferase (AST) ≥ 3 times the upper limit of normal (ULN) in the ubrogepant program. The purpose of this committee charter will be to provide a standardized process for the adjudication of data associated with these events in order to determine whether the elevation was related to ubrogepant.

An independent Data Safety Monitoring Board (DSMB) will also be established to review unblinded safety data and summary reports, identify any safety issues and trends, and make recommendations to the Sponsor, including modification or early termination of a trial, if emerging data show unexpected and clinically significant AEs of treatment.

Details of the DSMB memberships, standard operational procedures for data monitoring/review, frequency of review, and other pertinent details will be provided in a separate DSMB Charter.

4. Study Population and Entry Criteria

4.1 Number of Patients

Approximately 1650 patients will be randomized (550 patients per arm) from approximately 100 centers in the United States.

4.2 Study Population Characteristics

This study will include adult patients with migraine with or without aura.

4.3 Inclusion Criteria

To be eligible to participate in the study, patients must meet the following criteria:

1. Written informed consent and patient privacy information (eg, Written Authorization for Use and Release of Health and Research Study Information) obtained from the patient prior to initiation of any study-specific procedures
2. Male or female patients ages 18 to 75 years, inclusive, at Visit 1
3. At least a 1-year history of migraine with or without aura consistent with a diagnosis according to the International Classification of Headache Disorders, 3rd edition, beta version (ICHD-3 beta, 2013; Section 12.1.1)
4. Migraine onset before age 50
5. By history, the patient's migraines typically last between 4 and 72 hours if untreated or treated unsuccessfully and migraine episodes are separated by at least 48 hours of headache pain freedom
6. History of 2 to 8 migraine attacks per month with moderate to severe headache pain in each of the 3 months prior to Screening (Visit 1)

- 8. Be able to read, understand and complete the study questionnaires and eDiary.

4.4 Exclusion Criteria

Patients who meet any of the following criteria will not be eligible to participate in the study:

[Redacted]

- 10. Difficulty distinguishing migraine headache from tension-type or other headaches.

[Redacted]

- 12. Has taken medication for acute treatment of headache (including acetaminophen, nonsteroidal anti-inflammatory drugs [NSAIDs], triptans, ergotamine, opioids, or combination analgesics) on 10 or more days per month in any of the 3 months prior to Visit 1.

- 13. Has a history of migraine aura with diplopia or impairment of level of consciousness, hemiplegic migraine, or retinal migraine as defined by ICHD-3 beta (Section 12.1.1)

- 14. Has a current diagnosis of new persistent daily headache, trigeminal autonomic cephalgia (eg, cluster headache), or painful cranial neuropathy as defined by ICHD-3 beta (Section 12.1.1)

- 15. Required hospital treatment of a migraine attack 3 or more times in the 6 months prior to Visit 1.

[Redacted]

[Redacted]

17. Has a chronic non-headache pain condition requiring daily pain medication (with the exception of pregabalin)

[Redacted]

[Redacted]

[Redacted]

[Redacted]

[Redacted]

[Redacted]

[Redacted]

[Redacted]

[Redacted]

[Redacted]

[Redacted]

[Redacted]

[Redacted]

[Redacted]

[Redacted]

[Redacted]

[Redacted]

[Redacted]

[REDACTED]

[REDACTED]

[REDACTED]

[REDACTED]

[REDACTED]

[REDACTED]

[REDACTED]

[REDACTED]

[REDACTED]

[REDACTED]

[REDACTED]

[REDACTED]

- 28. History of malignancy in the 5 years prior to Visit 1, except for adequately treated basal cell or squamous cell skin cancer, or in situ cervical cancer
- 29. History of any prior gastrointestinal (GI) conditions (eg, diarrhea syndromes, inflammatory bowel disease) that may affect the absorption or metabolism of investigational product (IP); patients with prior gastric bariatric interventions (eg, Lap Band) which have been reversed are not excluded
- 30. History of acute hepatitis within 6 months of Screening (Visit 1) or chronic hepatitis (including nonalcoholic steatohepatitis) or a positive result on anti-hepatitis A immunoglobulin M (IgM) antibody, hepatitis B surface antigen, or anti-hepatitis C antibody testing at Screening (Visit 1)

[REDACTED]

[REDACTED]

[REDACTED]

[REDACTED]

[REDACTED]

[REDACTED]

[REDACTED]

[REDACTED]

4.5 Permissible and Prohibited Medications/Treatments

4.5.1 Permissible Medications/Treatments

Medications which are not specifically prohibited are allowed; however, there may be clarifications and restrictions with certain medications.

The following medications are allowed during the study, but are prohibited within 48 hours prior to taking IP:

- any triptan
- any ergot derivative
- any opioid
- any NSAID
- any other form of analgesic (including acetaminophen)
- any antiemetic agent
- any proton pump inhibitor

The following medications are allowed during the study, but are prohibited within 24 hours prior to taking IP:

- any antacid
- any H₂ blocker

Examples of allowed but restricted medications listed above are displayed in [Attachment 12.2](#).

Aspirin up to 325 mg/day is allowed for cardiac prophylaxis.

Daily use of pregabalin is allowed.

Selective serotonin reuptake inhibitors (SSRI) or serotonin norepinephrine reuptake inhibitors (SNRI) will be permitted provided that treatment is stable for at least 60 days prior to screening (Visit 1) and continues without change in dose throughout the study. SSRIs and SNRIs may not be started during the study.

Standard migraine prophylactic medications (eg, beta-blocker, tricyclic antidepressant, topiramate, valproic acid, botulinum toxin) will be permitted provided that the treatment is stable for at least 30 days prior to Visit 1, and continues without change in dose throughout the study. Prophylactic medications may not be started during the study.

Therapy considered necessary for the patient's welfare may be given at the discretion of the investigator. If the permissibility of a specific medication/treatment is in question, please contact Allergan.

4.5.1.1 Acute Treatment /Rescue Medication

Medications for acute treatment of migraine listed above may be taken during the study within the parameters noted in [Section 4.5.1.](#) [REDACTED]

[REDACTED]

[REDACTED] For details regarding the requirements for treatment with rescue medication and optional second dose, please refer to [Section 5.6.3.](#)

[REDACTED]

4.5.1.2 Definition of Females of (Non-)Childbearing Potential and/or Acceptable Contraceptive Methods

For purposes of this study, females will be considered of childbearing potential unless they are naturally postmenopausal (ie, no menses for 2 years) or permanently sterilized (ie, bilateral tubal ligation, bilateral salpingectomy, bilateral oophorectomy or hysterectomy).

For women of childbearing potential who may participate in the study, the following methods of contraception, if properly used, are generally considered reliable: hormonal contraceptives (ie, oral, patch, vaginal ring, injection, implant), male condom with

intravaginal spermicide, diaphragm or cervical cap with spermicide, intrauterine device, vasectomized partner, or sexual abstinence.

For males who may participate in the study, the following methods of contraception, if properly used, are generally considered reliable: post-bilateral vasectomy, barrier contraception, or sexual abstinence. Male participants must also refrain from donating sperm during the course of the study.

The investigator and each patient will determine the appropriate method of contraception for the patient during the participation in the study.

If a female becomes pregnant during the study, the investigator will notify Allergan immediately after the pregnancy is confirmed and the patient will be exited from the study after appropriate safety follow-up. The investigator will (1) notify the patient's physician that the patient was being treated with investigational drug ubrogepant, and (2) follow the progress of the pregnancy. The investigator must document the outcome of the pregnancy and provide a copy of the documentation to Allergan.

4.5.2 Prohibited Medications/Treatments

The following medications are prohibited 30 days prior to Visit 1 and throughout the study period:

- strong and moderate cytochrome P450 3A4 (CYP3A4) inhibitors, including but not limited to: systemic (oral/IV) itraconazole, ketoconazole, fluconazole; erythromycin, clarithromycin, telithromycin; diltiazem, verapamil; aprepitant; cyclosporine; nefazodone; cimetidine; quinine; and HIV protease inhibitors
- strong and moderate CYP3A4 inducers, including but not limited to: barbiturates (eg, phenobarbital and primidone), systemic (oral/IV) glucocorticoids, nevirapine, efavirenz, pioglitazone, carbamazepine, phenytoin, rifampin, rifabutin, and St. John's wort
- inhibitors of the BCRP (breast cancer resistance protein) transporter (eg, rifampicin)
- drugs with narrow therapeutic margins (eg, digoxin, warfarin)

Examples of prohibited medications in the classes noted above are displayed in [Section 12.2](#).

The decision to administer a prohibited medication/treatment is done with the safety of the study participant as the primary consideration. When possible, Allergan should be notified before the prohibited medication/treatment is administered.

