12.2 Examples of Prohibited Medications

Prohibited Medications

The following medications are prohibited 30 days prior to Screening and throughout the study period:

	Strong/Moderate CYP3A4 Inducers	Strong/Moderate CYP3A4 Inhibitors
Antidepressant/ Antianxiety	Barbiturates 
 • Amobarbital (Amytal[®]) • Aprobarbital (Alurate[®]) • Butalbital (Fiorinal[®], Fioricet[®]) • Butobarbital (Busodium[®], Butisol[®]) • Mephobarbital (Mebaral[®]) • Pentobarbital (Nembutal[®]) • Phenobarbital (Luminal[®], Solfoton[®]) • Secobarbital (Seconal[®]) 	Nefazodone (Serzone [®])
Antiseizure	Carbamazepine (Atretol [®] , Carbatrol [®] , Epitol [®] , Equetro [®] , Tegretol [®]) Oxcarbazepine (Trileptal [®]) Phenytoin (Dilantin [®] , Phenytek [®]) Primidone (Myidone [®] , Mysoline [®])	
Diabetes	Pioglitazone (Actos [®]) Troglitazone (Rezulin [®] , Resulin [®])	
Antiemetic		Aprepitant (Emend [®])
Antihypertension		Diltiazem (Cardizem [®]) Verapamil (Calan [®] , Calan SR [®])
Glucocorticoid (Systemic)	Betamethasone (Celestone [®]) Dexamethasone (Baycadron [®] , DexPak [®]) Hydrocortisone (Cortef [®]) Methylprednisolone (Medrol [®]) Prednisolone (Prelone [®]) Prednisone (Deltasone [®]) Triamcinolone (Kenalog [®])	
Antibiotics	Rifabutin (Mycobutin [®]) Rifampicin/ Rifampin (Rifadin [®] , Rifater [®] , Rimactane [®])	Erythromycin (Benzamycin [®] , EryTab [®]) Clarithromycin (Biaxin [®]) Telithromycin (Ketek [®])
Antifungal		Fluconazole (Diflucan [®] , Trican [®]) Itraconazole (Sporanox [®]) Ketoconazole (Nizoral [®])
Anti-HIV	Efavirenz (Stocrin [®] , Sustiva [®]) Nevirapine (Viramune [®])	Indinavir (Crixivan [®]) Nelfinavir (Viracept [®]) Ritonavir (Norvir [®]) Saquinavir (Fortovase [®] , Invirase [®])
Immunosuppressant		Cyclosporine - oral/IV only (Neoral [®] , Sandimmune [®])
Other	St John's Wort Enzalutamide (Xtandi [®]) Modafinil (Provigil [®])	Buprenorphine (Cizol [®] , Subutex [®] , Suboxone [®]), Quinine, armodafinil (Nuvigil [™])

Drugs with Narrow Therapeutic Margins	Warfarin (Coumadin [®]) Digoxin (Digitek [®] , Lanoxin [®] , Digox [®]) Cisapride (Prepulsid [®] , Propulsid [®]) Pimozide (Orap [®])
--	---

The following medications are allowed during the study; however, they are prohibited within 48 hours prior to taking IP:

Triptan	Almotriptan (Axert [®]) Eletriptan (Relpax [®]) Frovatriptan (Frova [®]) Naratriptan (Amerge [®]) Rizatriptan (Maxalt [®]) Sumatriptan (Imitrex [®]) Zolmitriptan (Zomig [®])

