Ergot Derivative	Dihydroergotamine (DHE 45 [®] , Migranal [®]) Ergotamine (Cafergot [®] , Ergomar [®] , Wigraine [®])
Opioid	Tramadol (eg, Ultracet [®] , Ultram [®]) Butorphanol (Stadol [®]) Codeine-containing analgesics (eg, Tylenol with Codeine #3 [®]) Hydrocodone (Zohydro ER [™])/Hydrocodone-containing analgesics (eg, Vicodin [®]) Oxycodone (Oxycontin [®] , Roxicodone [®])/Oxycodone-containing analgesics (eg, Percocet [®]) Morphine (MS Contin [®])
NSAID	Aspirin Combination medicines with NSAIDs (eg, Excedrin [®]) Diclofenac (Arthrotec [®] , Cataflam [®] , Voltaren [®]) Ibuprofen (eg, Advil [®] , Excedrin IB [®] , Motrin [®]) Ketoprofen (eg, Orudis [®]) Naproxen (eg, Aleve [®] , Naprosyn [®])
Analgesic	Acetaminophen (eg, Tylenol [®] or any combination drug Tylenol [®])
Antiemetic agent	Chlorpromazine (Thorazine [®]) Hydroxyzine (Vistaril [®]) Metoclopramide (Reglan [®]) Ondansetron (Zofran [®]) Prochlorperazine (Compazine [®]) Promethazine (Phenergan [®] , Mepergan [®])
Proton Pump Inhibitor	Esomeprazole (Nexium [®]) Lansoprazole (Prevacid [®] , Zoton [®]) Omeprazole (Losec [®] , Prilosec [®] , Zegerid [®]) Pantoprazole (Pantoloc [®] , Pantozol [®] , Protonix [®] , Somac [®] , Zurcal [®]) Rabeprazole (Aciphex [®] , Pariet [®] , Rabecid [®])

The following medications are allowed during the study; however, they are prohibited within 24 hours prior to taking IP:

Antacid	Aluminum Carbonate Gel (Basaljel [®]) Aluminium Hydroxide (AlternaGEL [®] , Amphojel [®]) Aluminium Hydroxide and magnesium hydroxide (Maalox [®] , Mylanta [®]) Bismuth Subsalicylate (Pepto-bismol [®]) Calcium Carbonate (Alcalak [®] , Quick-Eze [®] , Rennie [®] , Rolaid [®] , Titalac [®] , TUMS [®]) Hydrotalcite (Talcid [®]) Magaldrate plus Simethicone (Pepsil [®]) Magnesium Hydroxide (Phillips' Milk of Magnesia [®]) Sodium Bicarbonate (Alka-Seltzer [®] , Bicarbonate of Soda [®])
H₂ Blocker	Famotidine (Pepcid [®]) Nizatidine (Axiid [®]) Ranitidine (Zantac [®]) Cimetidine (Tagamet [®])

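### Cimetidine is barred for the whole study in Protocol Section 4.5.2 but allowed up to 24 hours before dosing in Attachment 12.2

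*Protocol*

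**What the plan says.** Section 4.5.2 of the protocol bars a set of drugs from 30 days before Visit 1 through the end of the study. The entry for strong and moderate CYP3A4 inhibitors names individual drugs and ends with "aprepitant; cyclosporine; nefazodone; cimetidine; quinine; and HIV protease inhibitors".

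Attachment 12.2 turns the rules into lists of examples. Its first table is headed "The following medications are prohibited 30 days prior to Screening and throughout the study period" and has a column for "Strong/Moderate CYP3A4 Inhibitors". Cimetidine is not in that column. A later table is headed "The following medications are allowed during the study; however, they are prohibited within 24 hours prior to taking IP", and its H2 blocker row includes "Cimetidine (Tagamet" with famotidine, nizatidine and ranitidine.

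Section 4.5.1 sets the general default, "Medications which are not specifically prohibited are allowed", and puts H2 blockers as a class under "The following medications are allowed during the study, but are prohibited within 24 hours prior to taking IP", without an exception for cimetidine.

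**The concern.** One drug, named in both places, has two rules, and a patient can comply with one while breaking the other. Sections 4.5.1 and 4.5.2 both send the reader to Attachment 12.2 for examples, so a site may well look a drug up there. A site that does so finds cimetidine named as usable and has no reason to look further.

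Three things follow. A recent cimetidine user may be enrolled at one site and turned away at another. A patient may take a drug that the protocol itself classes as a CYP3A4 inhibitor, which could change ubrogepant exposure. And the same use may or may not count as a protocol deviation, which matters because SAP Section 5.1.1.2.3 summarises major deviations by treatment group.

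**Working it through.** No sample size, power or alpha figure is involved, so the check is a comparison of the lists, name by name.

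**Step 1: the inhibitors named in Section 4.5.2.** There are 13 individual drugs: itraconazole, ketoconazole, fluconazole, erythromycin, clarithromycin, telithromycin, diltiazem, verapamil, aprepitant, cyclosporine, nefazodone, cimetidine and quinine. HIV protease inhibitors are added as a class.

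**Step 2: how many are in the Attachment 12.2 inhibitor column.** Twelve of the 13 are there, and four drugs stand for the HIV class (indinavir, nelfinavir, ritonavir, saquinavir). 13 − 12 = 1 missing: cimetidine.

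**Step 3: overlap between permitted and prohibited names.** Every drug named on the 48-hour and 24-hour lists of Attachment 12.2 was compared with every drug named as prohibited in Section 4.5.2 or Attachment 12.2. One drug is on both sides: cimetidine.

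**Step 4: the two rules applied to the same use.**

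| Cimetidine taken | Section 4.5.2 | Attachment 12.2 |
|---|---|---|
| 20 days before Visit 1 | Not allowed | Allowed |
| During the study, more than 24 hours before IP | Not allowed | Allowed |
| Within 24 hours before IP | Not allowed | Not allowed |
| During the study, after the dose | Not allowed | Allowed |

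The rules agree only in the 24 hours before dosing.

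**Step 5: how the protocol treats a comparable drug.** Aprepitant is also an inhibitor that belongs to a class allowed with restrictions, the antiemetics. Attachment 12.2 places "Aprepitant (Emend" in the prohibited inhibitor column and leaves it off the 48-hour antiemetic list. The named prohibition therefore overrides the class permission, and the attachment shows it. Cimetidine needed the same treatment and did not get it.

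**The case against.** The strongest reply is that the protocol already points to the answer. Section 4.5.1 allows only drugs that are not specifically prohibited, and Section 4.5.2 specifically prohibits cimetidine. Attachment 12.2 is cited only for examples, and an example should not override a named prohibition in the body. The rules are also nested: a patient who follows Section 4.5.2 automatically meets the 24-hour restriction. Sites are told to contact the sponsor when permissibility is in doubt, and concomitant medication is asked about at each visit. On this view the defect is one misplaced name in an attachment, with no consequence shown.

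Part of this stands. The default in Section 4.5.1 does settle a class permission against a named prohibition, so the unqualified H2 blocker entry there is a minor matter; aprepitant has no exception in that section either. Absence from a list of examples would not, alone, be an error. It is also true that no effect on the coprimary results is shown, and that the redacted exclusion criteria and the deviation specification, which is a separate document, cannot be consulted.

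The rest does not remove the conflict. Cimetidine is not merely left out of the prohibited examples; it is named among the permitted ones, and no visible text ranks the lists. The instruction to ask the sponsor helps only a site that sees a question. The 24-hour washout covers the period before dosing only: Attachment 12.2 would still permit cimetidine after the dose, when Section 4.5.2 bars it.

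**Conclusion.** The concern holds. The protocol gives two conflicting operating rules for cimetidine: 30 days before Visit 1 plus the whole study, against 24 hours before IP. The extent in the text is 1 of 13 individually named inhibitors, and the only drug on both sides. This should be fixed, because it bears on eligibility, exposure and deviation decisions.

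Its practical size is unknown: neither the number of cimetidine users nor the effect on ubrogepant exposure is given. No change to the coprimary inference, alpha or power is claimed. Recorded users can be found in the prior and concomitant medication summaries and listings (SAP Section 5.1.1.2.8). The conclusion rests on the visible text and assumes that no redacted passage settles which list governs. The documents do not prove which rule was intended; the aprepitant example and the default in Section 4.5.1 favour Section 4.5.2.

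**What to change.** Apply the Section 4.5.2 rule:

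- In Attachment 12.2, remove cimetidine from the H2 blocker row of the 24-hour list and add it to the strong/moderate CYP3A4 inhibitor column of the prohibited table.
- As a clarification, qualify the H2 blocker entry in Section 4.5.1 to except cimetidine and refer to Section 4.5.2.
- Use the same rule in the eligibility checks and in the Protocol Deviation Requirement Specification, and notify sites.

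If the sponsor's clinical pharmacology team did intend the 24-hour rule, delete cimetidine from Section 4.5.2 instead and leave Attachment 12.2 and Section 4.5.1 as they are. One rule has to be chosen and stated everywhere.

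The cost is an administrative protocol clarification and a site letter, with no change to sample size or analysis.
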